6.2 Navitoclax Dose modifications

The table below outlines the dose levels to be used for any necessary navitoclax dose modifications:

Version Date: July 22, 2022

Dose Level	Navitoclax Dose/Schedule
6	325 mg QD
5	300 mg QD
4	250 mg QD
3	200 mg QD
2	150 mg QD
1	100 mg QD

A maximum of three navitoclax dose level reductions are allowed. If a fourth dose level dose reduction is required, navitoclax will be permanently discontinued.

If navitoclax is held > 21 days, it should be discontinued.

6.2.1 Management of Thrombocytopenia

6.2.1.1 Dose Reduction and Interruption

Navitoclax accelerates apoptosis of circulating platelets, which differs from typical chemotherapy-induced thrombocytopenia related to myelosuppression.

All decisions regarding continued navitoclax dosing for individual subjects will be determined by the investigator, as appropriate. These decisions should be guided by the following:

Additional platelet counts should be performed every other day or at the discretion of the investigator for a platelet count on any given day that is less than 50,000/mm³.

Administration of navitoclax will be interrupted or discontinued for any pre-dose platelet count <25,000/mm³. A platelet count <25,000/mm³ should be confirmed the same day by a separate peripheral blood draw and sent also for a peripheral blood smear.

For any clinically significant bleeding event, defined as grade 2 or higher hemorrhage regardless of platelet count, navitoclax should be withheld, and:

- Once the toxicity recovers to an acceptable grade level (*i.e.*, \leq grade 1 bleeding and/or platelet count is \geq 50,000/mm³ and stable or increasing), navitoclax may be restarted at a reduced dose of DL -1.
- If the toxicity recurs at the dose levels above, navitoclax should once again be interrupted. Once the toxicity recovers to an acceptable grade level, navitoclax may be restarted at reduced dose of DL –2.
- If the toxicity recurs at the dose levels above, navitoclax should once again be interrupted. Once the toxicity recovers to an acceptable grade level, navitoclax may be restarted at DL –3 or stopped altogether.

After any grade 4 platelet count <25,000/mm³ is observed for the first time per month in a

Version Date: July 22, 2022

subject, serial PK samples will be collected. PK samples will be collected as soon as possible after the grade 4 platelet count is determined and then 24 and 48 hours after the event.

Limited human clinical data are available to understand the response to infusion of exogenous platelets in the presence of circulating drug levels. Data from a single dose and a 28-day multiple dose, nonclinical studies in dogs demonstrate that under conditions of navitoclax plasma concentrations exceeding concentrations in the clinic (>10 µg/mL) and rapid platelet apoptosis, platelet infusions do not have a measurable effect on circulating platelet counts. However, under conditions of lower navitoclax plasma concentrations (<10 µg/mL), platelet infusions do result in an increase in circulating platelet counts. This response appears to be more consistent and of greater duration as navitoclax plasma concentrations decline. Although the administration of multiple platelet transfusions may produce a sustained increase in circulating platelets, post-transfusion platelet kinetics should be monitored when clinically indicated. If platelet transfusions are required in response to active bleeding, dosing of navitoclax should be suspended. It should be noted that platelet response with transfusions may not follow typical platelet kinetics of thrombocytopenia as with typical chemotherapy-induced myelosuppression. Procedures consistent with local institutional blood banking guidelines regarding platelet transfusions should be followed.

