To reduce the incidence of significant thrombocytopenia associated with navitoclax dosing, a 7-day lead-in dosing period will be used for dose levels in which the target dose of navitoclax is greater than 150 mg daily (dose levels 3-7). Subjects will begin with navitoclax dosed at 150 mg PO daily and will escalate to the navitoclax dose defined in the cohort dose level after the 7th day of lead-in dosing if the subject's platelet count is ≥50,000/mm³ and the patient has no evidence of clinically significant bleeding, defined as grade 2 or higher hemorrhage regardless of platelet count. If the subject's platelet count on the 7th day of lead-in dosing is <50,000mm³, then the dose of navitoclax will be maintained at 150 mg daily for an additional 7 days. If the platelet count is <50,000mm³ after 14 days at the lead-in dose, then the lead-in dose will become the subject's dose for the duration of the study.

Two different schedules relating to the lead-in dosing period will be evaluated during Part 1 of this study. Schedule A will administer the 7-day lead-in dosing period of navitoclax as a single agent, prior to the initiation of trametinib dosing. Schedule B will begin the 7-day lead-in dosing period of navitoclax simultaneously with the initiation of trametinib dosing. Since potential drug interactions between trametinib and navitoclax are not yet defined, and since it is not yet known

Version Date: July 22, 2022

whether trametinib might potentiate the thrombocytopenia associated with navitoclax dosing, Schedule A (single agent lead-in) provides a potentially safer avenue for initial investigation of this combination. However, since navitoclax has not exhibited convincing single agent activity in pre-clinical models of KRAS mutant cancers ([name] et al., 2013), while trametinib has demonstrated activity in patients with KRAS mutant cancers (Infante et al, 2010; Messersmith et al., 2011), Schedule B may be preferable from an efficacy standpoint, as it does not delay the initiation of trametinib. Therefore, it will be important to determine if any meaningful differences in safety and tolerability exist between Schedules A and B. Schedule C (alternative dosing schedule with intermittent trametinib dosing) will be evaluated if unacceptable toxicity is observed during dose escalation on Schedules A or B. Schedules A, B and C are outlined below:

Schedule A Cycle 1 ONLY

Treatment day:

110	uuii	CIIt	uu.	, •																							

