1	2	3	4	5	6	7	8	9	10	11	12	13	14	15	16	17	18	19	20	21	22	23	24	25	26	27	28
							Т	T	Т	Т	Т	Т	T	Т	T	T	T	Т	Т	Т	Т	Т	T	Т	T	T	Т
L	L	L	L	L	L	L	N	N	N	N	N	N	N	N	N	N	N	N	N	N	N	N	N	N	N	N	N

Cycle 2 and Subsequent Cycles

Treatment day:

1	2	3	4	5	6	7	8	9	10	11	12	13	14	15	16	17	18	19	20	21	22	23	24	25	26	27	28
Т	Т	Т	Т	T	T	T	T	T	T	T	T	Т	T	T	T	T	T	T	T	T	T	T	Т	Т	T	T	Т
N	N	N	N	N	N	N	N	N	N	N	N	N	N	N	N	N	N	N	N	N	N	N	N	N	N	N	N

Schedule B Cycle 1 ONLY

Treatment day:

				/																							
1	2	3	4	5	6	7	8	9	10	11	12	13	14	15	16	17	18	19	20	21	22	23	24	25	26	27	28
Т	Т	Т	T	Т	Т	Т	T	T	Т	T	Т	Т	Т	Т	T	Т	Т	Т	Т	Т	Т	Т	T	Т	T	Т	Т
L	L	L	L	L	L	L	N	N	N	N	N	N	N	N	N	N	N	N	N	N	N	N	N	N	N	N	N

Version Date: July 22, 2022

Cycle 2 and Subsequent Cycles

Treatment day:

1	2	3	4	5	6	7	8	9	10	11	12	13	14	15	16	17	18	19	20	21	22	23	24	25	26	27	28
Т	Т	Т	Т	Т	Т	Т	Т	Т	Т	T	Т	Т	Т	Т	T	T	T	Т	T	Т	T	Т	Т	Т	T	Т	Т
N	N	N	N	N	N	N	N	N	N	N	N	N	N	N	N	N	N	N	N	N	N	N	N	N	N	N	N

Schedule C Cycle 1 ONLY

Treatment day:

1	2	3	4	5	6	7	8	9	10	11	12	13	14	15	16	17	18	19	20	21	22	23	24	25	26	27	28
Т	T	Т	Т	Т	Т	Т	Т	Т	Т	Т	Т	Т	Т														
L	L	L	L	L	L	L	N	N	N	N	N	N	N	N	N	N	N	N	N	N	N	N	N	N	N	N	N

Cycle 2 and Subsequent Cycles

Treatment day:

1	2	3	4	5	6	7	8	9	10	11	12	13	14	15	16	17	18	19	20	21	22	23	24	25	26	27	28
T	T	T	Т	Т	T	T	Т	T	T	Т	T	Т	Т														
N	N	N	N	N	N	N	N	N	N	N	N	N	N	N	N	N	N	N	N	N	N	N	N	N	N	N	N

T = trametinib dose defined by Phase 1b dose level or RP2D

L = lead-in dose of navitoclax (150 mg daily).

N = Navitoclax dose defined by Phase 1b dose level or RP2D. Note: as described above, after 7 days of navitoclax at the lead-in dose of 150 mg daily (L), dose will be escalated to the dose defined by the Phase 1b dose level or the RP2D (A), only if subject's platelet count is ≥50,000/mm³ and the patient has no evidence of clinically significant bleeding, defined as grade 2 or higher hemorrhage regardless of platelet count. If the subject's platelet count on the 7th day of lead-in dosing is <50,000mm³, then the dose of navitoclax will be maintained at 150 mg daily for an additional 7 days. If the platelet count is <50,000mm³ after 14 days at the lead-in dose, then the lead-in dose will become the subject's dose for the duration of the study.

Evaluation of dosing Schedules A and B will be performed according to the schema in **Figure 5.1.** Since it is not yet known whether drug interactions might occur between trametinib and

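### Section 6.2.1.1 joins bleeding and platelet recovery with and/or, so platelets alone literally permit navitoclax restart during the bleed that caused the hold

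*Combined protocol and SAP*

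**What the plan says.** **Hold and restart (Section 6.2.1.1).** Clinically significant bleeding is "defined as grade 2 or higher hemorrhage regardless of platelet count, navitoclax should be withheld". Navitoclax may be restarted one dose level down once the toxicity is back to an acceptable grade. A parenthesis introduced by *i.e.* defines that state: at or below "grade 1 bleeding and/or platelet count is" at least 50,000/mm³ and stable or increasing. Two further restart steps, for recurrences, use the same term without redefining it.

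Three other rules in the section bear on the point:
- A platelet floor of 25,000/mm³: "Administration of navitoclax will be interrupted or discontinued for any pre-dose platelet count" below that level.
- A transfusion rule: "If platelet transfusions are required in response to active bleeding, dosing of navitoclax should be suspended".
- An opening statement on discretion: "All decisions regarding continued navitoclax dosing for individual subjects will be determined by the investigator, as appropriate". The numbered thresholds are there to guide those decisions.

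**Lead-in (Sections 5.1.1 and 5.1.2, and the key to the schedule grids).** After 7 days at 150 mg, the dose steps up only if platelets are at least 50,000 and there is no grade 2 or higher hemorrhage. If the count is below 50,000, "then the dose of navitoclax will be maintained at 150 mg daily for an additional 7 days". If it is still below 50,000 after 14 days, 150 mg becomes the patient's "dose for the duration of the study".

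**The concern.** The hold is written to catch bleeding at any platelet count. The release, read as a definition, can be met on platelets alone. For a patient who bleeds with an adequate, steady count, the release condition is already satisfied when the hold begins.

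Such a bleed is plausible. Section 2.2.1.3 reports hemorrhage in 13% of trametinib patients against 0% on chemotherapy, mostly low grade, and the trametinib risk list in Section 7.1.1.1 notes fatal intracranial events. Section 6 says that when one drug is held the other continues unless its own criteria are met, so a patient held for bleeding may still be taking trametinib. At stake is re-exposure to navitoclax, whose primary dose-limiting toxicity is thrombocytopenia (Section 2.2.2), during an unresolved bleed.

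The lead-in rule raises a smaller question. Its instruction to stay at 150 mg for a count under 50,000 names no lower limit, and its bleeding condition bars only the step-up.

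**Working it through.** No sample size, power or alpha figure is involved. The check enumerates the rule and sets the sections side by side.

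**1. Enumerate the restart test.** Platelets are *adequate* when at least 50,000 and stable or increasing.

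| Bleeding | Platelets | Current test (either suffices) | Bleeding ≤ grade 1 required | Both required |
|---|---|---|---|---|
| ≤ grade 1 | adequate | restart | restart | restart |
| ≤ grade 1 | not adequate | restart | restart | no restart |
| ≥ grade 2 | adequate | **restart** | no restart | no restart |
| ≥ grade 2 | not adequate | no restart | no restart | no restart |

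The third row is the fault: it permits dosing in the state for which the same section orders a hold.

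**2. Does other text remove the third row?**
- The transfusion rule suspends dosing only when active bleeding needs platelets transfused. Other bleeds fall outside it.
- The 25,000 floor is irrelevant at 50,000 or more.
- Sections 5.1.1 and 5.1.2 join the same two conditions with *and*, but for the step-up decision, not for restart.
- Investigator discretion lets a site do the right thing. It does not correct the definition.

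**3. Which repair?** Requiring both conditions would also change the second row. Where the bleed has resolved and platelets sit at 25,000 to under 50,000, the current text permits restart, and patients without bleeding may be dosed at such counts. (Below 25,000 the floor stops dosing anyway.) Section 6.2 discontinues navitoclax held for more than 21 days, and 21/28 = 75% of one cycle, so a longer hold could cost an occasional patient the drug. Requiring only that bleeding be grade 1 or less corrects the third row and leaves the other three unchanged.

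**4. Lead-in rule against Section 6.2.1.1.**

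| Finding during lead-in | Sections 5.1.1 and 5.1.2 | Section 6.2.1.1 |
|---|---|---|
| 25,000 to under 50,000, no grade ≥ 2 bleed | continue 150 mg | no hold; extra counts |
| 25,000 to under 50,000, grade ≥ 2 bleed | continue 150 mg | withhold |
| under 25,000 | continue 150 mg | interrupt or discontinue |

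The last two rows conflict on their face. Section 6.2.1.1 is the better candidate to govern: it covers every pre-dose count and every significant bleed, with no exception for the lead-in. Section 5.1 refers dose modifications to Section 6, Section 5.2 does the same for management of DLT events, and Section 5.3.2 points to Section 6.2 for counts below 50,000. What is missing is a sentence in the lead-in rule itself that says so.

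**5. Statistical consequence.** Section 5.2 counts any grade 4 toxicity in the first 42 days as a DLT, and Section 6.2.1.1 treats a count under 25,000 as grade 4. That classification is the same under either wording. The two-stage design in Section 13.1.2 uses response counts. Neither edit touches these.

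**The case against.** The strongest defence of the restart rule is context. The sentence requires the toxicity to recover, and the toxicity is the bleed. The hold applies at any count, so restarting during a continuing grade 2 bleed would trigger it again at once. Restart is optional, at a reduced dose, and the investigator decides. The loose connective also has a sensible use: it allows restart when the bleed is over but platelets have not reached 50,000.

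Most of that stands, and it settles intent. A reader might infer that the protocol means to allow re-dosing through a bleed; the documents do not support that. But the parenthesis is the only definition of acceptable recovery, and on a bleeding rule a site should not have to infer that one of its two limbs does not mean what it says. The point about resolved bleeds also stands, and it argues against simply replacing the connective with *and*.

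On the lead-in, a reader might infer that these patients have no platelet floor and no bleeding protection. That too is unsupported. Section 6.2.1.1 covers them, the rule already bars step-up with significant bleeding, and extra monitoring applies below 50,000: "Additional platelet counts should be performed every other day or at the discretion of the investigator". One can fairly read the lead-in rule as assigning a dose level and Section 6 as governing holds from it. Only the unreconciled wording remains.

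**Conclusion.** The point holds as a patient-safety wording error in Section 6.2.1.1. As written, platelets of at least 50,000 and steady or rising satisfy the restart test during the grade 2 or higher bleed that caused the hold, contrary to the section's own premise. It rests on reading the *i.e.* parenthesis as the operative definition and *and/or* as inclusive.

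The size is one wrong row of four. The documents do not say how often a hold occurs at adequate platelets, or how often a lead-in count falls below 25,000 or comes with significant bleeding, so no number of affected patients can be given. Section 2.2.2 reports that the lead-in has reduced first-cycle grade 4 thrombocytopenia, which suggests that the lower lead-in counts may be uncommon.

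The lead-in conflict is secondary and minor, because Section 6 already governs. DLT counts, sample size and error rates do not change, and nothing here questions the validity of the design.

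**What to change.** **Section 6.2.1.1.** Replace the parenthesis with wording to this effect: *restart requires that bleeding has returned to grade 1 or less; platelet recovery alone is not sufficient. If the bleed has resolved and platelets are 25,000 to under 50,000/mm³, restart at the reduced dose is at the investigator's judgement.* The second sentence keeps what the current text allows, so holds after resolved bleeds are not lengthened toward the 21-day limit.

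**Sections 5.1.1 (text and schedule key) and 5.1.2.** Add *subject to 6.2.1.1* to the instructions to continue 150 mg and to keep it as the study dose.

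**Cost.** Wording in four places within one amendment, with no added visits, tests or patients. A patient still bleeding at grade 2 or higher with adequate platelets will stay on hold until the bleed settles, and the 21-day rule could then apply. That is the purpose of the hold.

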6.2.1.2 Platelet Transfusion Recommendations

If a platelet transfusion is deemed necessary, the investigator should be aware of the following:

- Due to the rapid apoptotic effect of navitoclax on mature platelets, the initial increase in platelet counts post-transfusion(s) may be smaller and the duration of response may be shorter. For this reason, the most recently collected donor platelets should be transfused.
- A post-transfusion platelet count should be obtained within 10 to 60 minutes.
- Additional transfusions may be necessary to achieve the desired platelet response.

6.2.2 Management of Lymphopenia

There is a potential for lymphopenia in this study. Anti-infective prophylaxis should be implemented at the investigator's discretion, including appropriate prophylaxis for viral, fungal, bacterial, or *Pneumocystis carinii Pneumonia* (PCP) infections. Potential for drug-drug interactions should be considered. See description of excluded and cautionary medications. Given the potential for increased thrombocytopenia associated with many of the agents used for PCP prophylaxis, investigators should consult with the principal investigator prior to initiating PCP prophylaxis.

6.2.3 Management of Neutropenia

Standard management practices for neutropenia should be followed. Preliminary data analysis from the ongoing phase 1 studies in subjects with CLL demonstrates an apparent trend in decreasing baseline-normalized absolute neutrophil count (ANC) nadir with increasing doses,

C_{max}, or AUC.

6.2.4 Management of Tumor Lysis Syndrome

In subjects with various tumor types, there is a potential for tumor lysis in the presence of risk factors such as bulky disease, elevated pre-treatment LDH levels, elevated leukocyte count, and dehydration. Adequate hydration, careful monitoring of laboratory values, and use of an agent to reduce the uric acid level should be considered for subjects at high risk in the first 4 weeks. For subjects who are at high risk during subsequent weeks, please consider the same management plan.

7. ADVERSE EVENTS: LIST AND REPORTING REQUIREMENTS

Adverse event (AE) monitoring and reporting is a routine part of every clinical trial. AEs will be collected and reported from the start of study treatment (first dose of study drug) and until the end of the follow up period as defined in section 5.5. The following list of AEs (Section 7.1) and the characteristics of an observed AE (Section 7.2) will determine whether the event requires expedited reporting (via CTEP-AERS) in addition to routine reporting.

7.1 Comprehensive Adverse Events and Potential Risks Lists (CAEPRs)

The Comprehensive Adverse Event and Potential Risks list (CAEPR) provides a single list of reported and/or potential adverse events (AE) associated with an agent using a uniform presentation of events by body system. In addition to the comprehensive list, a subset, the Specific Protocol Exceptions to Expedited Reporting (SPEER), appears in a separate column and is identified with *bold* and *italicized* text. The subset of AEs (SPEER) is a list of events that are protocol-specific exceptions to expedited reporting to NCI (except as noted below). Refer to the 'CTEP, NCI Guidelines: Adverse Event Reporting Requirements' http://ctep.cancer.gov/protocolDevelopment/electronic applications/docs/aeguidelines.pdf for further clarification. *Frequency is provided based on 968 patients*. Below is the CAEPR for Trametinib dimethyl sulfoxide (GSK1120212B).

NOTE: Report AEs on the SPEER ONLY IF they exceed the grade noted in parentheses next to the AE in the SPEER. If this CAEPR is part of a combination protocol using multiple investigational agents and has an AE listed on different SPEERs, use the lower of the grades to determine if expedited reporting is required.

7.1.1 CAEPRs for CTEP IND Agents

7.1.1.1 CAEPR for Trametinib

Comprehensive Adverse Events and Potential Risks list (CAEPR) for

Trametinib dimethyl sulfoxide (GSK1120212B, NSC 763093)

The Comprehensive Adverse Event and Potential Risks list (CAEPR) provides a single list of reported and/or potential adverse events (AE) associated with an agent using a uniform presentation of events by body system. In addition to the comprehensive list, a subset, the Specific Protocol Exceptions to Expedited Reporting (SPEER), appears in a separate column and is identified with bold and italicized text. This subset of AEs (SPEER) is a list of events that are protocol specific exceptions to expedited reporting to NCI via CTEP-AERS (except as noted below). Refer to the 'CTEP, NCI Guidelines: Adverse Event Reporting Requirements'

http://ctep.cancer.gov/protocolDevelopment/electronic_applications/docs/aeguidelines.pdf for further clarification. *Frequency is provided based on 1111 patients*. Below is the CAEPR for trametinib dimethyl sulfoxide (GSK1120212B).

NOTE: Report AEs on the SPEER ONLY IF they exceed the grade noted in parentheses next to the AE in the SPEER. If this CAEPR is part of a combination protocol using multiple investigational agents and has an AE listed on different SPEERs, use the lower of the grades to determine if expedited reporting is required.

Version 2.6, October 10, 20191 **Adverse Events with Possible** Specific Protocol Relationship to Trametinib (GSK1120212B) **Exceptions to Expedited** (CTCAE 5.0 Term) Reporting (SPEER) [n= 1111] Likely (>20%) Less Likely (<=20%) Rare but Serious (<3%) BLOOD AND LYMPHATIC SYSTEM DISORDERS Anemia (Gr 3) Anemia CARDIAC DISORDERS Heart failure Left ventricular systolic dysfunction Sinus bradycardia EYE DISORDERS Blurred vision Dry eye Eve disorders - Other (chorioretinopathy also known as retinal pigment epithelial detachment) Eve disorders - Other (retinal vein occlusion) Eye disorders - Other (visual disorders)2 Papilledema Periorbital edema GASTROINTESTINAL DISORDERS Abdominal pain Abdominal pain (Gr 2) Colitis Colonic perforation Constipation (Gr 2) Constipation Diarrhea (Gr 3) Diarrhea Dry mouth (Gr 2) Dry mouth

Adverse Events with Possible Relationship to Trametinib (GSK1120212B) (CTCAE 5.0 Term) [n= 1111]			Specific Protocol Exceptions to Expedited Reporting (SPEER)
Likely (>20%)	Less Likely (<=20%)	Rare but Serious (<3%)	
	Dyspepsia		Dyspepsia (Gr 2)
	Mucositis oral		Mucositis oral (Gr 3)
Nausea			Nausea (Gr 3)
Vomiting			Vomiting (Gr 3)
GENERAL DISORDERS AND ADMINISTRATION SITE CONDITIONS			
	Chills		Chills (Gr 2)
	Edema face		
Fatigue			Fatigue (Gr 3)
	Fever		Fever (Gr 2)
Generalized edema ³			Generalized edema ³ (Gr 2)
IMMUNE SYSTEM DISORDE			
	Allergic reaction ⁴		
INFECTIONS AND INFESTA			
	Folliculitis		Folliculitis (Gr 2)
	Lung infection		
	Paronychia		Paronychia (Gr 2)
	Skin infection		Skin infection (Gr 2)
INVESTIGATIONS			
	Alanine aminotransferase increased		Alanine aminotransferase increased (Gr 3)
	Alkaline phosphatase increased		Alkaline phosphatase increased (Gr 2)
	Aspartate aminotransferase increased		Aspartate aminotransferase increased (Gr 3)
	CPK increased		
	Ejection fraction decreased		
METABOLISM AND NUTRITION DISORDERS			
	Anorexia		Anorexia (Gr 3)
	Dehydration		Dehydration (Gr 3)
	Hypoalbuminemia		, , ,
	Hypomagnesemia		Hypomagnesemia (Gr 2)
	Hyponatremia		Hyponatremia (Gr 3)
MUSCULOSKELETAL AND	CONNECTIVE TISSUE DISOR	DERS	
	Arthralgia		
	Back pain		Back pain (Gr 2)
	Pain in extremity		Pain in extremity (Gr 2)
	,	Rhabdomyolysis	
NERVOUS SYSTEM DISORDERS			
	Dizziness		Dizziness (Gr 2)
	Headache		Headache (Gr 2)
RESPIRATORY, THORACIO	AND MEDIASTINAL DISORDI	ERS	
, , , , , , , , , , , ,	Cough		Cough (Gr 2)
	Dyspnea		Dyspnea (Gr 3)
		Pneumonitis	
SKIN AND SUBCUTANEOUS	S TISSUE DISORDERS		

Adverse Events with Possible Relationship to Trametinib (GSK1120212B) (CTCAE 5.0 Term) [n= 1111] Likely (>20%) Less Likely (<=20%) Rare but Serious (<3%)			Specific Protocol Exceptions to Expedited Reporting (SPEER)
	Alopecia	 	Alopecia (Gr 2)
	Dry skin		Dry skin (Gr 2)
	Nail changes		
		Palmar-plantar erythrodysesthesia syndrome	
	Pruritus		Pruritus (Gr 2)
		Skin and subcutaneous tissue disorders - Other (drug reaction with eosinophilia and systemic symptoms [DRESS])	
Skin and subcutaneous tissue disorders - Other (rash) ⁵			Skin and subcutaneous tissue disorders - Other (rash) ⁵ (Gr 3)
		Stevens-Johnson syndrome ⁶	
VASCULAR DISORDERS			
	Hypertension		Hypertension (Gr 3)
		Thromboembolic event (venous)	
	Vascular disorders - Other (hemorrhage) ⁷		

¹This table will be updated as the toxicity profile of the agent is revised. Updates will be distributed to all Principal Investigators at the time of revision. The current version can be obtained by contacting [contact]. Your name, the name of the investigator, the protocol and the agent should be included in the e-mail.

²Visual disorders include visual disturbance that can be associated with conjunctival hemorrhage, corneal graft rejection, cyclitis, eye nevus, halo vision, iritis, macular edema, retinal hemorrhage, visual acuity reduced, visual impairment, and vitreous detachment.

³Generalized edema includes edema, lymphedema, and edema limbs.

⁴Hypersensitivity (allergic reactions) may present with symptoms such as fever, rash, increased liver function tests, and visual disturbances.

⁵Skin and subcutaneous tissue disorders - Other (rash) may include rash, rosacea, rash acneiform, erythematous rash, genital rash, rash macular, exfoliative rash, rash generalized, erythema, rash papular, seborrhoeic dermatitis, dermatitis psoriasiform, rash follicular, skin fissures, and skin chapped.

⁶Stevens-Johnson syndrome has been observed in patients treated with trametinib and dabrafenib combination.

⁷The majority of hemorrhage events were mild. Major events, defined as symptomatic bleeding in a critical area or organ (e.g., eye, GI hemorrhage, GU hemorrhage, respiratory hemorrhage), and fatal intracranial hemorrhages have been reported.

Adverse events reported on trametinib dimethyl sulfoxide (GSK1120212B) trials, but for which

Version Date: July 22, 2022

there is insufficient evidence to suggest that there was a reasonable possibility that Trametinib dimethyl sulfoxide (GSK1120212B) caused the event:

BLOOD AND LYMPHATIC SYSTEM DISORDERS - Disseminated intravascular coagulation; Febrile neutropenia; Leukocytosis

CARDIAC DISORDERS - Atrial fibrillation; Cardiac arrest; Myocardial infarction; Restrictive cardiomyopathy, sinus tachycardia

EYE DISORDERS - Corneal ulcer; Eyelid function disorder; Flashing lights; Floaters; Glaucoma; Photophobia

GASTROINTESTINAL DISORDERS – Ascites; Duodenal ulcer; Esophageal necrosis; Esophageal ulcer; Esophagitis; Gastric hemorrhage; Gastric ulcer; Gastritis; Gastrointestinal disorders - Other (intestinal obstruction); Gastrointestinal disorders - Other (pneumatosis intestinalis); Gastrointestinal fistula; Gingival pain; Hemorrhoidal hemorrhage; Ileus; Obstruction gastric; Pancreatitis; Small intestinal obstruction; **GENERAL DISORDERS AND ADMINISTRATION SITE CONDITIONS** - Flu like symptoms; General disorders and administration site conditions - Other (axillary pain); Localized edema; Malaise; Noncardiac chest pain; Pain

HEPATOBILIARY DISORDERS – Cholecystitis; Hepatic failure; Hepatic pain; Hepatobiliary disorders - Other (hepatic encephalopathy)

INFECTIONS AND INFESTATIONS - Biliary tract infection; Catheter related infection; Device related infection; Endocarditis infective; Enterocolitis infectious; Hepatitis viral; Infections and infestations - Other (abscess limb); Infections and infestations - Other (necrotizing fasciitis); Infections and infestations - Other (oral infection); Pharyngitis; Sepsis; Upper respiratory infection; Urinary tract infection

INJURY, POISONING AND PROCEDURAL COMPLICATIONS - Bruising

INVESTIGATIONS - Blood bilirubin increased; Blood lactate dehydrogenase increased; Creatinine increased; Electrocardiogram QT corrected interval prolonged; GGT increased; Lipase increased; Lymphocyte count decreased; Platelet count decreased; Serum amylase increased; White blood cell decreased

METABOLISM AND NUTRITION DISORDERS - Hyperglycemia; Hyperkalemia; Hyperphosphatemia; Hyperuricemia; Hypocalcemia; Hypoglycemia; Hypokalemia;

MUSCULOSKELETAL AND CONNECTIVE TISSUE DISORDERS - Generalized muscle weakness; Musculoskeletal and connective tissue disorder - Other (compression fracture); Myalgia; Neck Pain NEOPLASMS BENIGN, MALIGNANT AND UNSPECIFIED (INCL CYSTS AND POLYPS) - Tumor hemorrhage; Tumor pain

NERVOUS SYSTEM DISORDERS - Dysgeusia; Encephalopathy; Intracranial hemorrhage; Lethargy; Nervous system disorders - Other (diplopia); Seizure; Somnolence; Stroke; Syncope; Transient ischemic attacks

PSYCHIATRIC DISORDERS - Anxiety; Confusion; Delirium; Depression; Hallucinations; Insomnia; Personality change

RENAL AND URINARY DISORDERS - Acute kidney injury; Cystitis noninfective; Dysuria; Hematuria; Proteinuria; Urinary incontinence

REPRODUCTIVE SYSTEM AND BREAST DISORDERS - Vaginal fistula; Vaginal hemorrhage **RESPIRATORY, THORACIC AND MEDIASTINAL DISORDERS** - Bronchopulmonary hemorrhage; Hypoxia; Laryngeal edema; Oropharyngeal pain; Pleural effusion; Pneumothorax; Productive cough; Pulmonary hypertension; Respiratory failure; Sinus disorder

SKIN AND SUBCUTANEOUS TISSUE DISORDERS - Bullous dermatitis; Photosensitivity; Purpura; Skin and subcutaneous tissue disorders - Other (erythema nodosum); Skin ulceration; Urticaria **VASCULAR DISORDERS** - Hematoma; Hot flashes; Hypotension;

Note: Trametinib dimethyl sulfoxide (GSK1120212B) in combination with other agents could cause an exacerbation of any adverse event currently known to be caused by the other agent, or the combination may result in events never previously associated with either agent.

